6.5.2.2.4 Reporting of hypoglycemic episodes

Hypoglycemic events and any associated symptoms are recorded only on the hypoglycemic episodes page of the CRF. Severe hypoglycemia and those episodes meeting any of the ICH

seriousness criteria ([Section 9.2.4](#)) are also to be notified as SAEs to the Mylan Global Product Safety and Risk Management department, as described in [Section 9.3.2.8](#); and entered on the SAE and AE pages.

6.5.2.3 Laboratory Safety

The following safety laboratory tests will be performed at times defined in the study schedules in [Sections 1](#) and [Section 6](#).

Table 4: Laboratory Safety Tests

Hematology	Chemistry	Urinalysis	Other
Hemoglobin	Urea and Creatinine	pH	Urine hCG
Hematocrit	Glucose	Glucose (qual)	HIV and HBsAg and
RBC count	Calcium	Protein (qual)	HCVAb
Platelet count	Sodium	Blood (qual)	HbA1c
WBC count	Potassium	Ketones	
Total neutrophils (Abs)	Chloride	Nitrites	
Eosinophils (Abs)	AST, ALT	Leukocyte esterase	
Monocytes (Abs)	Total Bilirubin	Microscopy/culture ^a	
Basophils (Abs)	Direct/Indirect bilirubin		
Lymphocytes (Abs)	Alkaline phosphatase		
	Uric acid		
	Albumin		
	Total protein		
	CRP		
	C-Peptide		
	Lipid Profile		

^a Only if urine dipstick is positive for blood, protein, nitrites or leukocyte esterase.

Hematology and chemistry will be analyzed by central laboratory. Urinalysis will be conducted by dipstick at site and if urine is positive for blood, protein, nitrites, or leukocyte esterase, will be analyzed via microscopy/culture by a central laboratory.

Blood volumes to be collected and blood and urine sample handling instructions will be provided in the central vendor laboratory manual. The central laboratory will provide collection materials and directions for packaging and shipment of samples.

Any clinically significant findings in laboratory safety data should be recorded as an AE. Determination of clinical significance and seriousness will be based on the Investigator's medical judgment.

6.5.2.4 Immunogenicity Assessment

Blood samples of 5 mL each will be taken into serum separator tubes at each time point as outlined in [Table 1](#). At Visits 1, 8, 10, 12, and 14, three blood samples will be drawn, whereas at Visit 6 (baseline) four blood samples will be drawn. The blood samples will be taken by direct venipuncture, and the exact times of blood sampling will be recorded in the CRF. Two of the samples will be used to determine the presence of anti-drug antibodies against insulin glargine using the approach outlined below. The other sample will be collected and stored in reserve for potential supplemental immunogenicity testing and/or characterization. Samples collected pre-dose at the randomization visit (Visit 6) will be considered as baseline. Samples collected at screening and the supplemental samples

collected at baseline may also be used for method development and validation. Sample handling instructions are specified in the laboratory manual.

A conventional radioimmunoassay will be employed for the assessment of anti-drug antibodies in clinical samples. In this assay, samples will undergo a pre-treatment step that includes acid dissociation to release any anti-insulin antibodies complexed with free drug, followed by charcoal adsorption of the free insulin analog. The treated samples will be incubated with a fixed amount of ^{125}I -MYL-1501D, and anti-drug antibody complex formation with the tracer is measured via gamma counter and expressed as a percentage of bound to total radioactivity (%B/T).

The multi-tiered sample analysis recommendations for immunogenicity testing from published white papers [7, 8], and current regulatory guidance [9, 10], will be employed for the immunogenicity assessment of MYL-1501D Process V and Process VI. The antidrug antibody analysis methodology will be fully validated, and the sample analysis procedures will be documented in a Sample Analysis Protocol. Sample handling, processing, and storage instructions will be detailed in a separate manual. The laboratory for immunogenicity analysis will be designated by the Sponsor.

6.5.2.4.1 PK Assessment

One blood sample of 4 mL will be taken into a K₂EDTA plasma tube at each time point, as outlined in [Table 1](#). The blood samples will be taken by direct venipuncture, and the exact times of blood sampling will be recorded in the CRF. The PK sample will be taken along with the immunogenicity samples. The exact time of last MYL-1501D dose prior to withdrawal of blood for PK will be noted. The blood samples will be analyzed for Insulin Glargine, Glargine M1 and M2 metabolite concentrations by Covance Laboratories Ltd. (Harrogate, UK) using a fully validated analytical method. Sample handling instructions are specified in the laboratory manual.

The PK samples are taken as outlined in [Table 1](#). The PK sample will be taken during the visit, preferably taken prior to the daily glargine dose. The timing of study drug administration from prior day should be collected along with the time of PK sample collection.

6.5.2.5 Blood Pressure and Pulse Rate

Blood pressure and pulse rate will be measured at times specified in [Sections 1](#) and [Section 6](#). Additional collection times, or changes to collection times of blood pressure and pulse rate will be permitted, as necessary, to ensure appropriate collection of safety data.

Blood pressure will be measured at sitting position, after 5 minutes rest.

The same size blood pressure cuff, which has been properly sized and calibrated, will be used to measure blood pressure each time. The use of automated devices for measuring blood pressure and pulse rate are acceptable, although, when done manually, pulse rate will be measured in the brachial/radial artery for at least 30 seconds. Any clinically significant changes in blood pressure and pulse rate should be recorded as an AE. Determination of clinical significance and seriousness will be based on the Investigator's medical judgment.

6.5.2.6 12-lead ECG

In this study, 12-lead ECGs will be recorded using local ECG devices and review. ECGs should be collected at times specified in the study schedules in [Sections 1](#) and [Section 6](#).

All scheduled ECGs should be performed after the subject has rested quietly for at least 5 minutes in a supine position.

To ensure safety of the subjects, a medically qualified individual at the site will assess ECG recordings and make any comparisons to baseline measurements.

In some cases, it may be appropriate to repeat abnormal ECGs to rule out improper lead placement as contributing to the ECG abnormality. It is important that leads are placed in the same positions each time in order to achieve precise ECG recordings. Any clinically significant ECG abnormalities measured at screening should be assessed for their effects on subject eligibility of the study and recorded in medical history. ECG parameters will not be recorded in the CRFs, but any clinical significant changes between the screening and subsequent ECGs should be recorded as an AE. Determination of clinical significance and seriousness will be based on the Investigator's medical judgment.

6.5.2.7 General Physical Examination

A full general physical examination will consist of an examination of the abdomen, cardiovascular system, lungs, lymph nodes, musculoskeletal and neurological systems, skin, extremities, head, ears, eyes, nose, and thyroid gland by trained medical personnel at the site. A full physical examination will be performed at Visit 1 (screening), Visit 6 (randomization) and Visit 14 (EOT or ET).

Height and weight will be assessed at Visit 1. Physical examination results will not be recorded in the CRFs, but any clinical significant finding at Screening (Visit 1) should be recorded under medical history and changes between Screening (Visit 1) and subsequent examinations should be recorded as an AE. Determination of clinical significance and seriousness will be based on the investigator's medical judgment.

7 STATISTICAL ANALYSIS

Detailed methodology for summary and statistical analyses of the data collected in this study will be documented in a Statistical Analysis Plan (SAP), which will be dated and maintained by the sponsor. This document may modify the plans outlined in the protocol; however, any major modifications of the primary endpoint definition and/or its analysis will also be reflected in a protocol amendment.

7.1 Sample Size Determination

A total of 202 subjects with T1DM are planned to be randomized for this study and will receive either MYL-1501D Process V product or MYL-1501D Process VI product, in a 1:1 ratio.

The sample size estimation is based on assumptions for the change from baseline up to week 18 in HbA1c with either MYL-1501D product from Process V or Process VI. It is assumed, that true mean groups mean difference is 0.03 and standard deviation is equal to 0.74. To demonstrate non-inferiority margin of 0.4% using a 2-sided 95% confidence interval and a 90% power, a total of 172 subjects (86 subjects per treatment group) are required.

To account for a maximum of 15% of subjects being not eligible for the per protocol analysis, a total sample size of 202 is planned to be randomized for this study. The true treatment difference and standard deviation is based on previous study MYL-GAIA-3001.

No replacement of subject will be performed if subject discontinued prematurely from the study.

7.2 Primary Endpoints

7.2.1 Definition of Primary Endpoints

The change in HbA1c from baseline up to week 18 is the primary endpoint for this study.

7.2.2 Statistical Methodology for Primary Endpoints

For the analysis of the primary endpoint all randomized subjects will be taken account – irrespective of whether subjects having post-baseline measurement. All scheduled non-missing data combined together with imputed missing data will be performed for primary analysis. Multiple imputed datasets will be generated based on the assumption of a monotone missing data pattern. The imputation will be performed using the monotone regression method for week 12 and week 18 sequentially. The variables treatment, pooled investigator, and basal insulin dose time will be used as independent variables.

Then the treatment effect will be estimated using a repeated measures analysis employing a restricted maximum likelihood (REML)-based, mixed model repeated measures (MMRM)-effects model approach. In this model all subjects will be used for the estimation of the 95% confidence interval of the difference between MYL-1501D Process VI product and Process V product for mean change in HbA1c at week 18. The MMRM model will include the fixed, categorical effect of treatment group assignment, visit, treatment group-by-visit interaction and the other fixed effect terms investigator, basal insulin dose time, and baseline HbA1c value as covariates.

Further details on the MMRM model will be provided in the SAP. Investigator pooling will be finalized before unblinding treatment to avoid introducing bias. The detailed method of investigator pooling will be documented in the SAP.

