7.5. STATISTICAL TESTS

The default significant level will be (5%); confidence intervals will be 95% and all tests will be two-sided, unless otherwise specified in the description of the analyses.

Non-inferiority will be tested at 2.5% (one-sided) level of significance.

Document: \sasdata\Mylan\Insulin_glargine\SYA22825\Biostatistics\Documentation\SAP\MYL-1501D-3004_SAP_Final_2_0_clean.doc

Author: [name]

Version Number:

2.0

Version Date:

18OCT2018

Template No: CS_TP_BS016 Revision 4
Effective Date: 01Apr2016

Reference: CS_WI_BS005

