Then, the remaining monotone missing data will be imputed using sequential regression multiple imputation, where a separate regression model is estimated for imputation of each variable (i.e., measurement at each visit) one after the other including the observed values and the values just imputed from the previous visit. Each regression model will include explanatory variables for pooled investigational sites, basal insulin dose time (morning vs. evening), treatment group and all previous (baseline (visit 6), week 12 (visit 12) and week 18 (visit 14)) values of HbA1c.

No rounding or range restrictions will be applied.

Imputed data will consist of 100 imputed datasets. The random seed number for the partial imputation with the MCMC method will be 20171220, and the random seed number for the sequential regression MI will be 171016.

Each of the 100 imputed datasets will be analyzed using the following analysis method. Change from baseline in HbA1c to each post-baseline visit will be calculated based on observed and imputed data. Mean changes from baseline in HbA1c values will be analyzed using a mixed model for repeated measures (MMRM) approach. Restricted maximum likelihood (ReML) estimation will be used. The MMRM model will include the changes from baseline in HbA1c values as dependent variables, the baseline HbA1c values as fixed covariate, pooled investigational sites, basal insulin dose time (morning vs evening), treatment group (MYL 1501D Process V and MYL 1501D Process VI), visit (week 12 and week 18), and treatment group by visit interaction as fixed effects, and subjects as random effect. An unstructured covariance structure will be used to model the within-subject error and the Kenward-Roger approximation will be used to estimate the degrees of freedom. If this analysis fails to converge, the following covariance structures will be tested: AR(1), ARH(1), CS, CSH, TOEP, TOEPH. The covariance structure converging to the best fit, as determined by Akaike's information criteria (AIC) will be used as the primary analysis.

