16.2.1. SECONDARY EFFICACY VARIABLES & DERIVATIONS

16.2.1.1. Fasting plasma glucose

The fasting plasma glucose is collected at baseline, week 2 (visit 8), week 6 (visit 10), week 12 (visit

Document:	\sasdata\Mylan\Insulin_glargine\SYA22825\Biostatistics\Documentation\SAP\MYL-1501D-3004_SAP_Final_2_0_clean.doc		
Author:	[name]	Version Number:	2.0
		Version Date:	18OCT2018
Template No:	CS_TP_BS016 Revision 4	Reference:	CS_WI_BS005
Effective Date:	01Apr2016		

Analysis Plan Template

12) and week 18 (visit 14, End of Treatment). The measurements are performed by the central laboratory Q2.

Actual values and changes from baseline at each time point will be computed and summarized by treatment group.

A separate analysis will be performed excluding patients with no fasting status.

16.2.1.2. Daily insulin dose per unit body weight (mealtime, basal insulin and total) for days of 8-point profiles

Patients will be asked to document the dose of insulin taken on the same day they will perform the 8-point SMBG profiles (from week -3 to week 18). The measurements are taken the week prior to the visits, so the week prior to:

- Week -3 (Visit 3)
- Week -2 (Visit 4)
- Week -1 (Visit 5)
- Week 0 (Visit 6)
- Week 6 (Visit 10)
- Week 12 (Visit 12)
- Week 18 (Visit 14)

Doses will be recorded in the patient's diary. This data will be transcribed to the eCRF after the patient diary is collected, by the investigator or designee at scheduled visits. The patient should document the 3 pre-visit estimations in the diary; and will be advised to document any additional estimations.

There will be three doses variables: meal time insulin dose, basal insulin and total insulin dose.

Daily Meal time insulin dose: is the sum of all the total daily meal time insulin (Humalog) dose over the double-blind treatment period divided by the number of days measured. For the computation of total daily mealtime doses, only the patients with at least three mealtime doses at a particular day are considered. That is, total daily mealtime dose will not be computed for a day if the mealtime dose is recorded less than 3 times for that day.

Daily Basal insulin dose: is the average of the insulin dose over days measured during the double-blind period.

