APPENDIX 3. SAS CODE EXAMPLE FOR MULTIPLE IMPUTATION

```
/* First, generate enough data to produce a monotone missing data pattern */
/* MCMC does not work with class statement. Pooled investigator sites and */
/* baseline insulin dose time have been converted to indicator variables */
/* For pooled investigator sites (sitegrln), */
/* let say that x is the total number of */
/* pooled investigator sites. Then, for pooled investigator sites #1, */
/* inv01=1, inv02=0, ..., inv0[x-1]=0 */
/* For pooled investigator sites #2, inv01=0, inv02=1, ..., inv0[x-1]=0 */
/* For pooled investigator sites #[x-1], inv01=0, inv02=0, ..., inv0[x-1]=1 */
/* For pooled investigator sites #x, inv01=0, inv02=0, ..., inv0[x-1]=0 */
/* For baseline insulin dose (strata) time= morning, binstime=1 */
/* For baseline insulin dose time= evening, binstime=0 */
/* No rounding or range is applied for any variable */
/* Non-informative prior is proc mi default MCMC prior information */
/* 200 is proc mi default number of burn-in iterations */

proc mi data = <<insert input dataset name>> out = datamono
    seed =20171220
    NIMPUTE=100;
    by trtpn;
    var inv01 inv02 ... inv0[x-1] binstime HbA1c_BASE HbA1c_WK12 HbA1c_WK18;
    mcmc impute = monotone chain= multiple;
run;

/* Then, do full imputation based on sequential regression models */
/* assuming monotone missing pattern. */
proc mi data = datamono seed = 171016 out = datami NIMPUTE = 1;
    by _imputation_;
    class trtp strata sitegr1;
    var trtp strata sitegr1 HbA1c_BASE HbA1c_WK12 HbA1c_WK18;
    monotone regression;
run;

/* Compute Changes from Baseline and create one categorical variables for */
/* the pooled investigational sites based on the [x-1] indicator pooled */
/* investigational site variables */
data datmichg;
    set datami (in=a drop = HbA1c_WK18 rename = (HbA1c_WK12 = result))
        datami (in=b drop = HbA1c_WK12 rename = (HbA1c_WK18 = result));

    * Visit;
    if a then visit = "Week 12";
    else if b then visit = "Week 18";
```

Document: \sasdata\Mylan\Insulin_glargine\SYA22825\Biostatistics\Documentation\SAP\MYL-1501D-3004_SAP_Final_2_0_clean.doc

Author: [name]

Version Number:

2.0

Version Date:

18OCT2018

Template No: CS_TP_BS016 Revision 4

Reference: CS_WI_BS005

Effective Date: 01Apr2016

Analysis Plan Template

* Change from baseline;
change = result - HbA1c_BASE;

run;

/* MMRM Analysis by _imputation_ */

```
proc sort data=datmichg;
  by _imputation_;
run;
```

```

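### The primary imputation uses no on-treatment glycaemic data before Week 12, although FPG is collected at Weeks 2 and 6; adding it is a cheap safeguard of low to moderate priority

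*Protocol*

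**What the plan says.** Protocol V2.0 section 7.2.2 imputes Week 12 and Week 18 in sequence and names three predictors: "The variables treatment, pooled investigator, and basal insulin dose time will be used as independent variables". It leaves model detail to the SAP. SAP V2.0 section 16.1.3 is the operative text: "Each regression model will include explanatory variables for pooled investigational sites, basal insulin dose time", together with treatment group and the HbA1c values at earlier visits. The regression step in Appendix 3 matches: "var trtp strata sitegr1 HbA1c_BASE HbA1c_WK12 HbA1c_WK18". The only post-baseline visits in the analysis model are Weeks 12 and 18.

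FPG is measured by the central laboratory. SAP 16.2.1.1 opens its list of visits with "The fasting plasma glucose is collected at baseline, week 2 (visit 8), week 6 (visit 10" and goes on to Weeks 12 and 18. FPG appears in none of the six PROC MI calls in Appendices 3 and 4.

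Three other provisions matter:

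- **Early termination (ET).** Protocol 6.3.7 repeats the Week 18 procedures, HbA1c included, at the ET visit. It asks subjects who stop study drug to keep attending.
- **Mapping.** SAP 7.3, worded for summary tables, moves an ET HbA1c to the next planned visit; its example sends a Visit 9 discontinuer's value to Visit 12. SAP 7.4, which sections 8.3 and 16.1.2 cite for the primary analysis, places it in its actual time window. Only days 76 to 91 reach Week 12.
- **Sensitivity analyses.** SAP 16.1.4 plans an analysis without imputation, one that adds 0.4 to imputed Process VI values, a two-arm tipping point, and LOCF.

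**The concern.** Imputation under missing-at-random is more credible the more it conditions on what was seen before the subject left. Here a subject without usable HbA1c from Week 12 on is drawn as a typical completer with the same baseline, arm, site and dose time, even when FPG at Weeks 2 and 6 shows control moving up or down. Because the imputation and the MMRM share the same variables, the imputation adds little to what the MMRM would give alone. Auxiliary variables are the main thing it could add.

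At stake is the Process VI minus Process V difference. If early leavers in one arm are systematically those with high FPG, that arm's mean is set too low. In Process VI this makes non-inferiority easier to declare; in Process V it makes it harder.

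**Working it through.** **Design inputs (Protocol 7.1, SAP 7.5).** "To demonstrate non-inferiority margin of 0.4% using a 2-sided 95% confidence interval and a 90% power, a total of 172 subjects"; "true mean groups mean difference is 0.03 and standard deviation is equal to 0.74"; "Non-inferiority will be tested at 2.5% (one-sided) level of significance"; "MYL-1501D Process V product or MYL-1501D Process VI product, in a 1:1 ratio"; 202 randomized, so 101 per arm.

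**The plan's own figure.** n per arm = 2 × 0.74² × (1.960 + 1.282)² / (0.4 − 0.03)² = 84.1, so 85 by the normal formula. The noncentral t gives 86 (power 90.3%), hence the stated 172. Then 172 / 0.85 = 202.35 against 202. The design reproduces, and this point does not change N. With no loss, the SE of the difference is 0.74 × √(2/101) = 0.1041.

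**Who is affected.** A subject who stops drug but attends Week 12 or 18 is not. A subject who leaves earlier with no HbA1c is. One with an ET HbA1c before day 76 depends on the mapping: SAP 7.3 would move the value to Visit 12 (for a subject stopping at Visit 9, as in its example), while under 7.4 it falls on a visit the model does not use, or in no window (for example days 46 to 62).

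**Closed-form extreme.** Suppose the fraction d of one arm with the highest FPG all leave, and FPG has correlation ρ with HbA1c change. Imputing them as completers shifts that arm's mean down by b = ρ × 0.74 × φ(z) / (1 − d), with z the 1 − d normal quantile. The one-sided error at a true difference of 0.4 is Φ(−1.96 + b/SE) if the arm is Process VI and Φ(−1.96 − b/SE) if it is Process V.

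- d = 0.05, ρ = 0.3: b = 0.3 × 0.74 × 0.1031 / 0.95 = 0.024; error 4.2% or 1.4%.
- d = 0.10, ρ = 0.5: b = 0.5 × 0.74 × 0.1755 / 0.90 = 0.072; error 10.3% or 0.4%.

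**Simulation with graded leaving.** Assumptions not in the documents: correlation 0.5, and log-odds of leaving rising 1.5 per SD of FPG in the arm or arms named. Setup: 101 per arm, SD 0.74, true difference 0.4, regression imputation with 20 draws and Rubin's rules, adjustment for treatment and baseline, 1,500 trials per row.

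| Loss | Leaving depends on FPG in | Bias, no FPG | Error, no FPG | Bias, with FPG | Error, with FPG |
|---|---|---|---|---|---|
| 5% | Process VI only | −0.029 | 4.7% | −0.005 | 2.7% |
| 5% | Process V only | +0.024 | 1.6% | 0.000 | 2.8% |
| 5% | both | 0.000 | 2.4% | 0.000 | 1.6% |
| 10% | Process VI only | −0.046 | 7.0% | −0.002 | 2.9% |
| 10% | Process V only | +0.047 | 0.6% | +0.002 | 2.0% |
| 10% | both | +0.001 | 2.3% | 0.000 | 2.5% |

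Monte Carlo error is about 0.4 percentage points near 2.5% and 0.7 near 7%. Other runs of the same kind, at correlations 0.3 to 0.5 and losses of 5 to 10%, gave −0.011 to −0.041 (error 3.1 to 5.6%) for Process VI only, and +0.015 to +0.047 (0.7 to 2.0%) for Process V only. At 15% loss the table's setup gives −0.064 (8.9%) and +0.066 (0.7%). Under random loss of 10%, adding FPG moves the SE only from 0.1053 to 0.1038.

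**What the margin-added analysis recovers.** Adding 0.4 to a fraction d of Process VI moves its mean up by 0.4d. For the Process VI rows: −0.029 + 0.020 = −0.009 at 5%, and −0.046 + 0.040 = −0.006 at 10%. Full correction would need shifts of 0.029/0.05 = 0.58 and 0.046/0.10 = 0.46, which the tipping point can reach.

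**The case against.** The strongest reply is that the affected group may be very small and that nothing in the documents points to a direction. Subjects who stop drug are asked to stay, ET visits include HbA1c, and those who switch to Lantus under the Week 12 rescue criterion already have a Week 12 HbA1c as predictor. The trial is double-blind with identical pens, PK/PD equivalence of the two processes has been reported, and treatment is in the imputation model. The withdrawal criteria in Protocol 4.2.3 do not name hyperglycaemia; the glycaemic ones are severe hypoglycaemia and hypoglycaemic unawareness. Leaving for low glucose, if concentrated in Process VI, would bias against non-inferiority. Auxiliary variables are a refinement whose absence breaks no rule, and the sensitivity analyses already cover this departure.

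Most of this stands. A reader might infer that the omission favours non-inferiority, or that everyone leaving before Week 12 is imputed from baseline alone. The documents support neither: the first needs unequal dependence on FPG in one particular direction, and the second overlooks continued attendance and the ET sample.

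Two parts do not stand. Under SAP 7.4 an ET HbA1c before day 76 is unused in the primary analysis, so the ET visit does not protect the model as it first appears to. And the sensitivity analyses do not alter the decision, which rests on the primary confidence interval.

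**Conclusion.** The gap is real and cheap to close; priority is low to moderate. The imputation omits relevant data already collected, and for subjects without usable Week 12 or 18 HbA1c it relies on baseline HbA1c, arm, site and dose time alone.

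The size rests on inputs the documents do not give: the loss before Week 12, the correlation of early FPG with HbA1c change, and how leaving depends on FPG in each arm. The 15% in Protocol 7.1 is an allowance for per-protocol ineligibility, not early loss; the expectation of under 5% with missing values stands only in superseded Protocol V1.0. At 5 to 10% loss and correlation 0.3 to 0.5, bias is about 0.01 to 0.05 in either direction and the one-sided error runs from below 1% to about 7%. With equal dependence in both arms, or none, it is negligible. The simulations are simpler than the planned analysis (20 rather than 100 imputations, one post-baseline outcome, no site term), so the figures show scale only. The case for change is that FPG removes nearly all the simulated bias whichever arm it comes from, without widening the SE.

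**What to change.** 1. In SAP 16.1.3 and Protocol 7.2.2, add FPG at baseline, Week 2, Week 6 and Week 12 as auxiliary variables in the imputation model only. Order the VAR lists by time: baseline HbA1c and FPG, FPG Weeks 2 and 6, HbA1c Week 12, FPG Week 12, HbA1c Week 18.
2. Make the change in all six PROC MI calls of Appendices 3 and 4, including the two fallback calls and the round/min/max lists, with no rounding or limits on FPG.
3. Leave the MMRM unchanged. Set non-fasting FPG to missing inside the imputation, and discard imputed FPG afterwards so that the FPG endpoints stay unimputed as Protocol 7.3 requires. Add a clause to Protocol 7.2.5 permitting this.
4. Reconcile SAP 7.3 with 7.4 on where an ET HbA1c before day 76 goes in the primary analysis. This concerns the endpoint itself, so it may matter more than FPG.
5. Restore the ridge prior in the Appendix 3 fallback: section 16.1.3 promises it, but the V2.0 code comments it out.

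**Cost.** No new data. The per-arm MCMC step grows from 17 variables (13 site indicators, dose time, three HbA1c values) to 21, with some added convergence risk. The change should be fixed before unblinding, with a protocol amendment if it counts as major under Protocol section 7. At the least, pre-specify the FPG version as a sensitivity analysis and settle the mapping.
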